10.3 Analysis of Laboratory Data

10.3.1 Variables and Units

All laboratory parameters to be collected in this study are listed below. Laboratory parameters will be reported using the standard international (SI) units.

Table 6. List of Laboratory Variables

Laboratory Variables
Hematology
White Blood Cell (WBC) Count
Red Blood Cell (RBC) Count
Hemoglobin
Hematocrit
Platelets count
Neutrophils
Basophils
Eosinophils
Lymphocytes
Monocytes
Reticulocytes
Bands
Chemistry
Total Bilirubin
Alkaline Phosphatase (ALP)
Serum glutamic oxaloacetic transaminase (SGOT/AST)
Serum glutamic pyruvic transaminase (SGPT/ALT)
Total Protein
Albumin
Glucose
Triglycerides
Blood Urea Nitrogen (BUN)
Creatinine
Uric acid

Table 6. List of Laboratory Variables (Continued)

Laboratory Variables
Chemistry (Continued)
Sodium
Potassium
Calcium
Inorganic Phosphorus
Creatine Phosphokinase (CPK)
Chloride
Bicarbonate
Cholesterol
LDL cholesterol
HDL cholesterol
Urinalysis
Specific Gravity
pH
Protein
Glucose
Ketones
Blood
Microscopic Examination
Immunologic Laboratory Assessments
Rheumatoid Factor (RF)
Anti-CCP antibody
Advanced Lipid Panel
Apo A1
Apo B
Other
hSCRp
HBs Ab
HBc Ab
Hbs Ag

Table 6. List of Laboratory Variables (Continued)

Laboratory Variables
Other (Continued)
HBV DNA PCR reflex only
HCV Ab
HCV RNA reflex only
QuantiFERON-TB Gold

10.3.2 Assessment of Mean Change from Baseline in Clinical Laboratory Values

Analyses of mean change from baseline in continuous hematology, chemistry, and urinalysis variables which are measured longitudinally will be performed by visits and by treatment group. For each change from baseline analysis, the following summary statistics will be presented for each treatment group sequence: sample size, baseline mean, visit mean, and the mean, standard deviation, and median of the changes from baseline.

10.3.3 Assessment of Shift from Baseline in Clinical Laboratory Variables

The baseline and post-baseline laboratory observations will be categorized as Grade 1, Grade 2, Grade 3, and Grade 4 according to OMERACT criteria (Rheumatology Common Toxicity Criteria v.2.0). For creatine phosphokinase and creatinine NCI CTC criteria will be used.

For each laboratory variable, shift tables will be generated that cross tabulate the subjects as deemed appropriate by treatment sequence:

- Category of the baseline value versus category of the final value.
- Category of the baseline value versus maximum category.
- Category of the baseline value versus minimum category.

Note that the minimum/maximum category is used, rather than the category of the minimum/maximum value. The two may be different due to variation in the reference range.

No statistical tests will be performed for this analysis.

10.3.4 Potentially Clinically Significant Laboratory Values

The criteria for potentially clinically significant laboratory values will be determined by OMERACT criteria of Grade 3 or 4. For creatine phosphokinase, creatinine, and parameters that are not covered in the OMERACT criteria, NCI CTC criteria will instead be used. For laboratory parameters where values available, a listing of all subjects with any laboratory determination during each period meeting OMERACT criteria of Grade 3 or 4 will be provided by Grade. For each of these subjects, the whole course of the respective parameter will be listed.

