**5.2.2                    Exclusion Criteria**

1. Pregnant or breastfeeding female.
2. Ongoing infections at Week 0 that have NOT been successfully treated. Subjects with ongoing infections undergoing treatment may be enrolled BUT NOT dosed until the infection has been successfully treated.
3. Anticipated requirement or receipt of any live vaccine during study participation including up to 30 days after the last dose of study drug.
4. Laboratory values from the visit immediately prior to Baseline Visit\* meeting the following criteria:
  - Serum aspartate transaminase (AST) or alanine transaminase (ALT) > 3.0 × ULN
  - Estimated glomerular filtration rate by simplified 4-variable Modification of Diet in Renal Disease (MDRD) formula < 40 mL/min/1.73m^2

- Total white blood cell count (WBC) < 2,000/ $\mu$ L
- Absolute neutrophil count (ANC) < 1,000/ $\mu$ L
- Platelet count < 50,000/ $\mu$ L
- Absolute lymphocytes count < 500/ $\mu$ L
- Hemoglobin < 8 gm/dL

\*Local requirements may apply. Refer to [Appendix N](#) for local requirements (United Kingdom).

5. Enrollment in another interventional clinical study while participating in this study.
6. Consideration by the investigator, for any reason, that the subject is an unsuitable candidate to receive study drug.

Criteria	Rationale
-----------------	------------------

- |       |  |
|-------|--|
| 1     | The impact of upadacitinib on pregnancy and nursing is unknown |
| 2 – 6 | To ensure safety of the subjects throughout the study          |

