10.0 Safety Analysis

10.1 General Considerations

Safety analyses will include reporting of adverse events, laboratory, and vital signs measurements in open-label treatment period only. Safety analyses will be carried out using the Open-Label Treated Population, which includes all subjects who received at least one dose of open-label study medication.

Long-term safety analyses include reporting of AE rate adjusted by cumulative exposure, mean change from baseline in laboratory parameters and vital sign variables, and frequency of potentially clinically significant laboratory and vital signs values.

The treatment-emergent adverse event (TEAE) rate per 100 patient-years of exposure will be presented by the exposure groups defined in Section 8.1, namely

1. Upadacitinib 6 mg BID/15 mg QD
2. Upadacitinib 12 mg BID/30 mg QD
3. Upadacitinib 6 mg BID/15 mg QD post down titration
4. Any upadacitinib

Listing of subjects with TEAEs by SOC and PT will be provided. Frequency tables and listings of subjects meeting criteria for potentially clinically significant vital sign values and for potentially clinically significant laboratory values will be provided by the exposure groups defined in Section 8.1.

Mean changes from baseline in all continuous laboratory parameters and vital signs variables at each visit will be summarized by the treatment group sequences defined in Section 9.1, namely

1. Upadacitinib never titrated (6 mg BID/15 mg QD),
2. Upadacitinib titrated up and not down (6 mg BID/15 mg QD to 12 mg BID/30 mg QD), and
3. Upadacitinib titrated up and down (6 mg BID/15 mg QD to 12 mg BID/30 mg QD and then back down to 6 mg BID/15 mg QD).

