10.4 Analysis of Vital Signs and Weight

10.4.1 Variables and Criteria Defining Abnormality

Vital sign variables include sitting systolic blood pressure, sitting diastolic blood pressure, pulse, body temperature, and weight. The criteria for potentially clinically significant vital sign findings are presented in [Table 7](#).

Table 7. Criteria for Potentially Clinically Significant Vital Sign Findings

Vital Sign	Category	Criteria for Potential Clinically Significant Vital Signs
Systolic blood pressure	Low	Value ≤ 90 mmHg and decrease ≥ 20 mmHg from Baseline
	High	Value ≥ 160 mmHg and increase ≥ 20 mmHg from Baseline
Diastolic blood pressure	Low	Value ≤ 50 mmHg and decrease ≥ 15 mmHg from Baseline
	High	Value ≥ 105 mmHg and increase ≥ 15 mmHg from Baseline
Weight	High	> 7% increase from baseline
	Low	> 7% decrease from baseline

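### The laboratory frequency tables by exposure group count any Grade 3–4 value, so for lymphocytes and parameters without an entry limit, abnormalities present at baseline are mixed with new ones

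*SAP*

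**What the plan says.** SAP 10.3.4 sets the laboratory criterion: "The criteria for potentially clinically significant laboratory values will be determined by OMERACT criteria of Grade 3 or 4". NCI CTC grades replace OMERACT for CPK, creatinine and parameters that OMERACT does not cover. The listing follows the same rule: "a listing of all subjects with any laboratory determination during each period meeting OMERACT criteria of Grade 3 or 4 will be provided by Grade". It adds: "For each of these subjects, the whole course of the respective parameter will be listed".

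SAP 10.1 carries the criterion into tables and says that results for "potentially clinically significant laboratory values will be provided by the exposure groups defined in Section 8.1". The scope is "laboratory, and vital signs measurements in open-label treatment period only". No section adds a condition on baseline grade.

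Four other places bear on the point:
- SAP 5.2 takes baseline as the last value on or before the first dose in the preceding randomized trial (RCT).
- SAP 10.3.3 cross-tabulates baseline grade against final, maximum and minimum grade, by treatment sequence.
- SAP Table 7 flags low systolic pressure only for "Value ≤ 90 mmHg and decrease ≥ 20 mmHg from Baseline". The other blood-pressure rules have the same two parts, and the weight rules are changes from baseline.
- SAP 10.2 counts an event that predates the first open-label dose as treatment-emergent only if its severity later increases.

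**The concern.** Vital signs and adverse events are both judged against the subject's earlier state, but a laboratory value qualifies on its grade alone. A subject who was at Grade 3 before the first RCT dose and stays there is counted in the same cell as one who fell to Grade 3 on upadacitinib.

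Long-term safety is part of the primary objective, and lymphopenia and raised CPK are adverse events of special interest. A reader of the table by exposure group will take its counts as findings arising at that dose. The share that was already present need not be equal across the groups. Everyone starts in the lower-dose group. Entry to the higher-dose group follows inadequate response, and entry to the post-down-titration group can follow a safety concern, a toxicity-management threshold or, since Amendment 5, the investigator's discretion.

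**Working it through.** The plan states no rate, power or sample size for this table, so there is no figure to reproduce. The check has four steps.

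**1. Which parameters are affected?** Grade 3–4 cut-offs (SAP Appendix C) are set against the exclusions in Protocol 5.2.2. Appendix N words the laboratory criterion differently for the United Kingdom; the main text is used here.

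| Parameter | Grade 3–4 begins at | Excluded at entry | Still open? |
|---|---|---|---|
| Neutrophils (×1000) | 0.9 and below | < 1.0 | No |
| White cells (×1000) | 1.9 and below | < 2.0 | No |
| Platelets (×1000) | 49.9 and below | < 50 | No |
| AST / ALT | 3.1 / 3.0 × ULN | > 3.0 × ULN | No, except ALT at exactly 3.0 |
| Hemoglobin, absolute part | below 8.0 g/dL | < 8 g/dL | No |
| Lymphocytes (×1000) | 0.9 and below | < 0.5 | Yes, 0.5–0.9 |
| CPK, bilirubin, alkaline phosphatase, uric acid, glucose, electrolytes | various | no limit | Yes |

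The lymphocyte exclusion reads "Absolute lymphocytes count < 500" per µL, while Grade 3 is 500–900. Hemoglobin is otherwise graded on the fall from pre-treatment, and creatinine Grade 3 can be met as more than 3.0 × baseline, so those two already carry a comparison with baseline.

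**2. Is one subject counted more than once?** The exposure groups in SAP 8.1 divide a subject's time. A subject titrated up and then down contributes to groups 1, 2 and 3, and again to group 4 (any upadacitinib). A persistent abnormality can appear in each.

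**3. Would a persistent abnormality be picked up?** Assume a stable personal mean of 0.85 ×1000 lymphocytes, a lognormal within-subject CV of 15%, and independent visits.
- σ = √ln(1 + 0.15²) = 0.149; μ = ln 0.85 − σ²/2 = −0.174.
- P(one value < 0.9) = Φ((ln 0.9 + 0.174)/0.149) ≈ 0.68.
- P(at least one in 13 visits) = 1 − 0.32¹³ > 0.999. With all 27 visits of SAP Table 1 it is higher still.

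Such a subject is almost certain to be counted, with no change in level.

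**4. How much could it matter?** Let b be the share at Grade 3–4 at baseline whose abnormality persists, and q the new-onset rate among the rest. The SAP rule gives b + (1 − b)q, of which (1 − b)q is new. Both b and q are assumptions. With q = 2% and all 494 enrolled subjects as denominator:

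| b | Pre-existing, 494 × b | SAP rule | Of which new |
|---|---|---|---|
| 0.5% | 2.5 | 2.49% | 1.99% |
| 1% | 4.9 | 2.98% | 1.98% |
| 3% | 14.8 | 4.94% | 1.94% |
| 5% | 24.7 | 6.90% | 1.90% |
| 10% | 49.4 | 11.80% | 1.80% |

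**The case against.** **Baseline grade is already shown.** The shift tables use the same grades and the same population. Their baseline rows give the number already at Grade 3–4, and summing the three sequences gives baseline-to-worst shifts for any upadacitinib. The listing gives every flagged subject's full course. This stands, and it confines the gap to the three dose-specific exposure groups. It does not close the gap: sequences classify subjects, exposure groups classify time, and one cannot be rebuilt from the other. A listing lets a reader check individuals but leaves the counts unchanged.

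**The plan does not call these values treatment-emergent, and an inclusive display suits a long-term safety study.** This is right for the listing, which should stay. It is weaker for a frequency table set out by dose, where the comparison between columns invites attribution.

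**A worsening rule does not remove noise.** With the step 3 assumptions but a stable mean of 1.1 (Grade 2), the chance of at least one value below 1.0 is 0.988 over 13 visits and 0.9999 over 27. That subject would still count as worsened. True; the rule removes one source of mixing, not all.

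**The vital-sign rules are not a contradiction.** Table 7 needs its own cut-offs, while laboratory values use an established toxicity scale. Accepted; the contrast shows only that the plan uses change from baseline elsewhere.

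**A reader might infer that the lymphocyte limit shows subjects had Grade 3 lymphopenia before any study drug.** The documents do not support that. The limit applies at the visit just before the extension's Baseline Visit, after the RCT, whereas analysis baseline precedes the RCT. A Grade 3 value at entry may have arisen on upadacitinib during the RCT.

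**Conclusion.** The point holds in a limited form. As written, the frequency tables by exposure group count any Grade 3–4 value without asking whether it is worse than baseline. For lymphocytes and for parameters with no entry limit, they can therefore mix pre-existing with new abnormality, and can repeat one subject across groups.

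The size is unknown. The 2–49 subjects and the inflation from about 2% to between 2.5% and 11.8% rest on assumed values of b and q and on full persistence. How far the mixing differs between exposure groups cannot be estimated from the documents.

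Two broader readings go too far. One is that every laboratory parameter is affected whatever the baseline: hemoglobin and creatinine are partly graded against baseline, and the entry limits largely close Grade 3–4 at entry for neutrophils, white cells, platelets and transaminases. The other is that these tables are the main display of laboratory safety: the SAP does not say so, and sets them beside mean changes, shift tables, liver criteria and rates for events of special interest. This is a cheap improvement to interpretability, not a flaw that undermines the safety analysis.

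**What to change.** In SAP 10.3.4 and 10.1, for the frequency tables by exposure group only, count subjects with a post-baseline Grade 3–4 value of a higher grade than their baseline grade. Show alongside, in each group, the number already at Grade 3–4 at baseline. Splitting the table by baseline grade (below 3 versus 3–4) would serve equally well. Use the baseline of SAP 5.2, so that a decline during the RCT still counts as worsening.

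Keep the listing of all subjects with any Grade 3–4 value, with its whole course, unchanged.

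The cost is a sentence in the SAP, one programming condition and one extra row, with no new data. The downside is that a subject who deteriorates within a grade appears only in the listing and in the row for baseline Grade 3–4.

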#### **6.4 Adverse Events of Special Interest**

The following AEs of special interest will be monitored during the study (see detailed toxicity management in Section 6.10):

- Serious infections, opportunistic infections, herpes zoster, and active TB;
- Malignancy (all types);
- Adjudicated Gastrointestinal perforations;
- Adjudicated cardiovascular events (e.g., major adverse cardiovascular event [MACE]);
- Anemia;
- Neutropenia;
- Lymphopenia;
- Increased serum creatinine and renal dysfunction;
- Hepatic events and increased hepatic transaminases;
- Increased creatine phosphokinase (CPK);

- Adjudicated cardiac, embolic and thrombotic events (non-cardiac, non-CNS).

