
**Table 5. Specific Toxicity Management Guidelines for Abnormal Laboratory Values (Continued)**

Laboratory Parameter	Toxicity Management Guideline
Serum Creatinine	
 
If serum creatinine is <math>> 1.5 \times</math> the baseline value and <math>> \text{ULN}</math>, repeat the test for serum creatinine (with subject in an euvoletic state) to confirm the results. If the results of the repeat testing still meet this criterion, then interrupt study drug and re-start study drug once serum creatinine returns to <math>\leq 1.5 \times</math> baseline value and <math>\leq \text{ULN}</math>
 
If confirmed serum creatinine <math>\geq 2 \text{ mg/dL}</math>, interrupt study drug and re-start study drug once serum creatinine returns to normal reference range or its baseline value.
 
For the above serum creatinine elevation scenarios, complete supplemental renal eCRF.
 

Creatine Phosphokinase	
 
If confirmed CPK value <math>\geq 4 \times \text{ULN}</math> and there are no symptoms suggestive of myositis or rhabdomyolysis, the subjects may continue study drug at the investigator's discretion.
 
If CPK <math>\geq 4 \times \text{ULN}</math> accompanied by symptoms suggestive of myositis or rhabdomyolysis, interrupt study drug and contact AbbVie Therapeutic Area Medical Director.
 
For the above CPK elevation scenarios, complete supplemental CPK eCRF.
 

\* Local requirements may apply. Refer to [Appendix N](#) for local requirements (United Kingdom).

If the subject must undergo elective surgery, the study drug should be interrupted at least 1 week prior to the surgery. If the subject must undergo emergency surgery, the study drug should be interrupted at the time of the surgery. The study drug can recommence once the physician has examined the surgical site and determined that it has healed and there is no sign of infection.

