10.2.4 Frequent Adverse Events by System Organ Class and Preferred Term

TEAEs occurring at ≥ 2 E/100PY in any of the exposure groups will be summarized by MedDRA PT in decreasing rate.

10.2.5 Adverse Events of Special Interests Rates per 100 Patient-Years of Study Drug Exposure

The Adverse Events of Special Interests (AESI) categories will be summarized and presented for each exposure group using SOC and MedDRA PT. The AESI categories will be identified per Standard MedDRA Queries (SMQs)/Company MedDRA Queries (CMQs) in [Table 5](#) below. Adjudicated cardiovascular events will be summarized and presented by treatment groups using CAC adjudicated categories.

Table 5. AESI for Upadacitinib with SMQs/CMQs/PTs Searches

AESI	Type of MedDRA Query	Broad or Narrow Search	SMQ/CMQ Search Criteria
Serious Infections	CMQ		"Infections" – Subset for SAEs
Opportunistic Infection excluding Tuberculosis and Herpes Zoster	CMQ		"Opportunistic Infection excluding Tuberculosis and Herpes Zoster"
Possible Malignancy	SMQ	Narrow	"Malignancies"
Malignancy	SMQ		"Malignant tumours"
Non-Melanoma Skin Cancer (NMSC)	SMQ	Narrow	Skin Malignant tumours (Narrow SMQ) removing Melanoma CMQ
Malignancy excluding NMSC			"Malignant tumours" SMQ removing NMSC output
Lymphoma	SMQ		"Malignant Lymphomas"
Hepatic Disorder	SMQ	Narrow	"Drug Related Hepatic Disorders"
Adjudicated Gastrointestinal Perforations	Output from adjudication		
Anemia	CMQ		"Non-Hemolytic and Non-Aplastic Anemias"
Neutropenia	CMQ		"Hematological Toxicity – Neutropenia"
Lymphopenia	CMQ		"Hematological Toxicity – Lymphopenia"
Herpes Zoster	CMQ		"Herpes Zoster"
Creatine Phosphokinase (CPK) Elevation	PT		Search only for the PT of "Blood creatine phosphokinase increased"
Renal Dysfunction	SMQ	Narrow	"Acute Renal, Failure"
Active Tuberculosis	CMQ		"Active Tuberculosis"
Adjudicated Cardiovascular Events	Output from CAC		
MACE*			
Cardiovascular Death			
Non-fatal Myocardial Infarction			
Non-fatal Stroke			

Table 5. AESI for Upadacitinib with SMQs/CMQs/PTs Searches (Continued)

AESI	Type of MedDRA Query	Broad or Narrow Search	SMQ/CMQ Search Criteria
Undetermined/Unknown Cause of Deaths			
Other Cardiovascular events			
Adjudicated Thrombotic Events	Output From CAC		
Venous Thromboembolic Events**			
Deep Vein Thrombosis			
Pulmonary Embolism			
Other Venous Thrombosis			
Arterial Thromboembolic Events (non-cardiac, non-neurologic)			

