** In L14, 1.1 – 2.0 × ULN is changed to 1.1 – 1.5 × ULN.

*** In L3, L7 and L8, mg/dl is changed to mmol/l.

**** For CPK and Creatinine NCI CTC grading will be used. For CPK therefore the following gradings apply: Grade 1: > ULN – 2.5 × ULN; Grade 2: > 2.5 – 5.0 × ULN; Grade 3: > 5.0 – 10.0 × ULN; Grade 4: > 10.0 × ULN; For Creatinine the following gradings apply: Grade 1: > 1 – 1.5 × Baseline; > ULN – 1.5 × ULN; Grade 2: > 1.5 – 3.0 × Baseline; > 1.5 – 3.0 × ULN; Grade 3: > 3.0 baseline; > 3.0 – 6.0 × ULN; Grade 4: > 6.0 × ULN.

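### Creatinine rises that interrupt study drug under Protocol Table 5 but stay below Grade 3 are not counted in the SAP's exposure-group laboratory table, and the SAP's AESI table has no row for increased serum creatinine

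*SAP*

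**What the plan says.** **Counting rule.** SAP 10.3.4 sets the laboratory flag: "The criteria for potentially clinically significant laboratory values will be determined by OMERACT criteria of Grade 3 or 4". It then makes an exception: "For creatine phosphokinase, creatinine, and parameters that are not covered in the OMERACT criteria, NCI CTC criteria will instead be used". SAP 10.1 puts the resulting frequency tables and listings in the exposure groups of SAP 8.1, which follow the dose being taken.

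**Creatinine grades.** The Appendix C note gives "Grade 2: > 1.5 – 3.0 × Baseline; > 1.5 – 3.0 × ULN" and then "Grade 3: > 3.0 baseline; > 3.0 – 6.0 × ULN; Grade 4: > 6.0 × ULN".

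**Protocol action.** Table 5 in Protocol 6.10 has two creatinine criteria. One is a value above 1.5 times baseline that also exceeds ULN: "If the results of the repeat testing still meet this criterion, then interrupt study drug". The other is a confirmed value of 2 mg/dL or more. Both allow restart on recovery, and both require a supplemental renal eCRF.

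**AESI.** Protocol 6.4 lists "Increased serum creatinine and renal dysfunction". In SAP 10.2.5, Table 5, the only renal row is a narrow standard MedDRA query, "Acute Renal, Failure". CPK elevation, by contrast, has its own preferred-term row.

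**The concern.** Long-term safety is part of the primary objective, and the exposure groups are how the SAP relates safety findings to dose. Protocol Table 5 treats a confirmed creatinine rise of this size as reason to interrupt drug, yet the SAP's exposure-group count starts at a higher level.

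The gap is nearly specific to creatinine. The global Table 5 triggers for hemoglobin, neutrophils, lymphocytes, white cells and platelets all fall in OMERACT Grade 3 or 4. ALT and AST have their own exposure-group table in SAP 10.3.5, starting at 3 times ULN. Creatinine has neither.

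At stake is whether a difference between dose levels in moderate creatinine rises can be read from an objective laboratory count, or only from what sites chose to report as adverse events.

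**Working it through.** There is no sample size or power figure to reproduce; the check compares cut-offs.

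**Inputs from the documents**
- Protocol Table 5, criterion A: above 1.5 × baseline and above ULN. Criterion B: 2 mg/dL or more.
- SAP Appendix C note: Grade 3 is above 3.0 × baseline or above 3.0 × ULN. I read the two limbs as alternatives. Requiring both would raise the Grade 3 entry and widen the gap.

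**Assumptions (not in the documents)**
- ULN 0.9 to 1.3 mg/dL and baseline 0.4 to 1.2 mg/dL.
- The same baseline value is used in both rules.

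**Formulas**, with b = baseline
- First trigger = min(max(1.5b, ULN), 2.0)
- Grade 3 entry = min(3.0b, 3.0 × ULN)

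| b (mg/dL) | ULN (mg/dL) | First trigger | Grade 3 entry | Uncounted band |
|---|---|---|---|---|
| 0.4 | 1.3 | 1.30 | 1.20 | none |
| 0.5 | 1.1 | 1.10 | 1.50 | 1.10 to 1.50 |
| 0.7 | 1.1 | 1.10 | 2.10 | 1.10 to 2.10 |
| 0.8 | 1.1 | 1.20 | 2.40 | 1.20 to 2.40 |
| 1.0 | 1.1 | 1.50 | 3.00 | 1.50 to 3.00 |
| 1.2 | 0.9 | 1.80 | 2.70 | 1.80 to 2.70 |
| 1.2 | 1.3 | 1.80 | 3.60 | 1.80 to 3.60 |

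Over 5 ULN values × 8 baselines = 40 combinations, the band is empty in two, both with b = 0.4 (ULN 1.2 and 1.3), where ULN is at least 3b. Where 1.5b is at least ULN and b does not exceed ULN, Grade 3 starts at 3.0/1.5 = 2 times the trigger.

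**Criterion B.** 2.0/3.0 = 0.67, so 2 mg/dL lies below Grade 3 when baseline and ULN are both at least 0.67 mg/dL. Below that baseline, 2 mg/dL is already Grade 3.

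**The OMERACT reading.** The listing sentence in SAP 10.3.4 says OMERACT Grade 3 or 4 without repeating the NCI CTC exception. OMERACT Grade 3 creatinine starts at 1.9 × ULN. With ULN 1.1 that is 2.09 mg/dL, against a first trigger of 1.20 at b = 0.8. A gap therefore remains, though a narrower one. It closes only when 1.5b reaches 1.9 × ULN, that is b at or above 1.27 × ULN.

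**Where a Grade 2 rise does appear**
- Shift tables (SAP 10.3.3): all four grades, by treatment sequence.
- Mean change by visit (SAP 10.3.2): by treatment sequence.
- TEAE tables by preferred term (SAP 10.2.2): by exposure group, if reported as an event.

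A subject whose creatinine rises on 6 mg BID and who later goes to 12 mg BID sits in the titrated-up sequence. The shift table cannot show which dose was being taken at the rise. Only the never-titrated sequence is free of this.

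**How often a trigger stays below Grade 3.** The documents give no distribution. Two assumed tails for the ratio to baseline show the range for P(above 3 × | above 1.5 ×):
- Pareto, 0.5^a with a = 1 to 4: 50%, 25%, 12.5%, 6.25%.
- Log-normal centered on no change, log-SD up to 0.5: at most 6.7%.

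The share staying below Grade 3 is thus anywhere from 50% to over 99%, set entirely by the assumption.

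**CPK.** Grade 3 is above 5.0 × ULN and the protocol threshold is 4 × ULN, so the band is 4.0 to 5.0 × ULN.

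**The case against.** The strongest reply is that an action threshold and a reporting threshold serve different purposes. An interruption rule can be precautionary, and nothing in the protocol ties the term potentially clinically significant to Table 5. Protocol 8.1.6.3 asks for abnormal-value frequencies, normal-range shifts and listings, not counts at action levels. This stands, and it is why the point is an improvement and not an error in the grading.

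The data are also not lost. Grade 2 values reach the shift tables, and a reported event reaches the preferred-term tables by exposure group. A value leading to study discontinuation or needing treatment is an adverse event. Protocol 6.3.1 also has a parenthetical pointing to the Section 6.10 criteria, which might make interruptions reportable, but its wording is unclear. SAP 10.2.1 and 10.2.5 allow extra event summaries. All this stands, but it leaves the by-dose view dependent on site reporting.

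Protocol 8.1.6.2.1 names renal dysfunction and increased CPK for AESI summaries, with no creatinine item, and the SAP rows match it. That list is expressly not exhaustive, so it does not remove the item in Protocol 6.4.

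A reader might infer more than the documents support:
- That such subjects are usually missed: no frequency is given, and the range above rests on assumed tails.
- That the renal AESI search misses them: the contents of the query are not in the documents.
- That they are permanently off drug: Table 5 interrupts and allows restart.
- That raised creatinine is a known class effect: Protocol 3.2 reports it for tofacitinib in some subjects, as typically reversible and without overt renal decline.
- That CPK is equally affected: the band is narrow, subjects without symptoms may continue, and the CPK AESI search has no grade limit.

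**Conclusion.** The point holds for creatinine. A confirmed rise that interrupts drug but stays below Grade 3 is absent from the exposure-group table of potentially clinically significant laboratory values. The remaining laboratory outputs cannot place it at the dose being taken for subjects whose dose changed. Separately, the SAP's AESI table does not carry the increased serum creatinine item of Protocol 6.4, and whether the narrow renal query covers it cannot be determined from the documents.

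The gap typically runs from 1.5 to 3 times baseline; its mg/dL limits depend on the assumed ULN and baseline. The number of subjects in it is unknown. This is more than preference, because the SAP already gives liver tests lower exposure-group cut-offs and the protocol singles out creatinine as an AESI. It is a worthwhile, low-cost improvement; it does not invalidate the safety analysis.

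**What to change.** 1. In SAP 10.3.4, beside the Grade 3 and 4 rows, add counts and percentages by exposure group for the protocol's existing creatinine criteria: above 1.5 × baseline and above ULN (any, and confirmed on repeat), and 2 mg/dL or more. State which baseline applies, since SAP 5.2 uses the pre-RCT value and Protocol Table 5 does not specify. State how confirmation is identified from repeat samples, and give the SI equivalent of 2 mg/dL, since SAP 10.3.1 reports in SI units.
2. In SAP 10.2.5, Table 5, add a preferred-term row for increased serum creatinine, as is done for CPK, so that the AESI list matches Protocol 6.4.
3. Reconcile the listing sentence in SAP 10.3.4, which names OMERACT, with the NCI CTC rule for creatinine and CPK.
4. Optional: a row for CPK at 4 × ULN or more. The UK white-cell trigger (below 2,500/μL, reaching into OMERACT Grade 2) could be handled the same way.

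The cost is a few table rows from laboratory and adverse event data already collected, and a higher count of flagged values. No clinical threshold or management rule changes.
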